#### 4.3.2. Subgroup Efficacy Analyses

Summary statistics for the change from baseline in uPCR (Schedule A) over time will be reported for subpopulations of participants defined by the following baseline characteristics:

- Screening uPCR ( $\leq 2.0$  and  $> 2.0$  g/g)
- Region (Japan and ROW)
- Baseline eGFR (30-45 and 45+ mL/min/1.73 m^2)
- Baseline Gd-IgA1 ( $\leq 50^{\text{th}}$  and  $> 50^{\text{th}}$  percentile  $\mu\text{g/mL}$ )
- Baseline BMI ( $< 30$  and  $\geq 30$  kg/m^2)
- Baseline Total IgA ( $\leq 50^{\text{th}}$  and  $> 50^{\text{th}}$  percentile ug/ml)
- Baseline APRIL ( $\leq 50^{\text{th}}$  and  $> 50^{\text{th}}$  percentile pg/mL)

The following subgroup analysis will be performed only if  $\geq 10$  participants fulfill the 'yes' category at baseline:

- ACEi/ARB therapy at enrollment (yes/no)

- Use of steroid and/or any immunosuppressive therapy prior to enrollment (yes/no)
- Tonsillectomy prior to enrollment (yes/no)
- SGLT2 inhibitor use (yes/no)
- Prior Hypertension (yes/no)

#### 4.3.3. Sensitivity Efficacy Analyses

There will be 3 sensitivity analyses:

Sensitivity Analysis 1: the primary analysis ([Section 4.3.1](#)) performed on the PP population.

Sensitivity Analysis 2: the primary analysis ([Section 4.3.1](#)) performed on uPCR from Schedule B collections.

Sensitivity Analysis 3: the analysis of covariance (ANCOVA) model will be used to compare the treatment effects in uPCR (Schedule A) on the natural log scale between treatment groups at 12 months as a sensitivity analysis. The ANCOVA model will be fitted with treatment group, strata, and baseline uPCR (Schedule A) on the natural log scale. The outputs are the same with those estimated from the primary efficacy model for each treatment group.

### 4.4. Analysis of Secondary Efficacy Endpoints

Secondary analyses will be conducted using the mITT population, unless otherwise specified.

#### 4.4.1. Secondary Efficacy Analyses

All secondary endpoints, as well as the respective changes from baseline, for each parameter will be summarized descriptively over time by treatment group, including number and percentage of participants with missing or incomplete assessments at that visit, for the following endpoints:

- 24-hour urine protein excretion (mg/day)
- eGFR (mL/min/1.73 m^2)
- Total serum IgA, IgG, and IgM concentrations (mg/dL) in the PD population

The uPCR (Schedule A; up to Month16), urine protein excretion (up to Month 16) will be summarized, at each specified time point, between placebo and VIS649 dose levels of 2, 4, and 8 mg/kg, respectively.

##### 4.4.1.1. uPCR (from 24-hour urine collection or the intended 24-hour urine collection) at Months 9 and 16

The treatment effect for each treatment group and the treatment difference at Month 9 will be generated from the same MMRM applied in the primary efficacy analysis ([Section 4.3.1](#)). The

outputs for Month 9 are included with those from the primary efficacy analyses. The Month 16 outputs will be generated from the MMRM including Months 9, 12, and 16 (Schedule A).

#### 4.4.1.2. 24-hour Urine Protein Excretion

The MMRMs will be fitted to estimate the treatment difference for the 24-hour urine protein excretion at Months 9, 12, and 16, respectively. Since the distribution of 24-hour urine protein excretion is skewed, the response variable will be the natural log transformed ratio of 24-hour urine protein excretion. The models will include the treatment group, strata, categorical visit, treatment-by-visit, and natural log transformed baseline 24-hour urine protein excretion as covariates. The model for Months 9 and 12 will include Baseline, Months 9 and 12. The model for Month 16 will include Baseline, Months 9, 12 and 16. The treatment differences on these assessments at Months 9, 12, and 16 will be estimated from their respective models by the differences in the geometric mean ratio reduction, along with the SEs, 95% CIs, and p-values.

24-hour Urine Protein Excretion that is unable to be calculated because the total protein excretion is below the lower limit of quantification (LLOQ) will be noted in the associated listing as such. Statistical summary tables that include imputed values will be indicated in the footnotes. The LLOQ for this test is [REDACTED]. Values that are below the limit of quantification (BLQ) will be substituted with [REDACTED] for the statistical summaries and the calculation of descriptive statistics.

#### 4.4.1.3. eGFR

MMRMs will be fitted to estimate the treatment difference for the eGFR at Months 12 and 16, respectively. The models will include the treatment group, strata, categorical visit, treatment-by-visit interaction, and baseline eGFR as covariates. The model for Month 12 will include all timepoints from baseline through Month 12. The model for Month 16 will include all timepoints from baseline through Month 16. The treatment effect on these assessments at Months 12 and 16 will be estimated by the LS means and their differences in the LS means, along with the SEs, 95% CIs, and p-values.

Change from baseline eGFR (LS mean  $\pm$ SE) will be displayed graphically across time by line chart for all visits up to Month 16.

#### 4.4.1.4. eGFR Linear Slope

The eGFR linear slope from baseline to Month 12 and 16 will be derived from the slope value of a linear regression of baseline through Months 12 and 16 eGFR, respectively across time (days), per subject, using the linear model  $eGFR = a + b(\text{days})$  where b is the linear slope value. The eGFR slope, up to Months 12 and 16, will be compared between placebo and VIS649-treated groups using an ANCOVA model with baseline eGFR as covariate.

---

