- ⁷ The dose of study intervention will be based on the M0 predose weight.
- ⁸ The comprehensive list of serum chemistry tests to be performed is provided in [Appendix 2](#). A full serum chemistry panel will be obtained at screening and on M0, M3, M6, M9, M12, and M15; the following tests are required at other visits: sodium, potassium, chloride, bicarbonate, blood urea nitrogen, creatinine, and glucose. Local laboratory assessments may be performed at Investigator discretion throughout the study in the course of patient care (but not assessments that would potentially unblind treatment status, such as measurement of immunoglobulin levels). Any clinically significant abnormalities should be recorded in the eCRF.
- ⁹ The comprehensive list of hematology tests to be performed is provided in [Appendix 2](#).
- ¹⁰ The comprehensive list of urinalysis tests to be performed is provided in [Appendix 2](#). On days of 24-hour urine collection, the uPCR sample will be collected from the 24-hour urine collection and routine urinalysis will be performed on a sample freshly voided during the clinic visit.
- ¹¹ Participants will discard the first void and begin a 24-hour urine collection the day prior to the clinic visit. For all 24-hour urine collection, the following parameters will be obtained or derived: 24-hour urine volume, protein, albumin, and creatinine, uPCR, and uACR.
- ¹² Samples should be taken from the 24-hour urine sample.
- ¹³ Up to 60 participants (approximately 15 per cohort) may have a more extensive PK and PD sampling schedule, as described in [Table 5](#). Study participants agreeing to participate in this more intensive PK and PD sample collection sub-study will sign an additional informed consent for this activity.
- ¹⁴ Blood samples to be collected before and after study intervention infusion at all visits.
- ¹⁵ Samples for ADA assessment will be collected before the start of infusion.
- ¹⁶ Samples for evaluation of host genetic markers related to IgAN susceptibility loci, the APRIL/BAFF pathway, and/or immunity will be collected before the start of infusion.
- ¹⁷ On days of 24-hour urine collection, urine samples for exploratory biomarker analysis will be collected and stored from a sample freshly voided during the clinic visit.

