#### 1.1.2.4. Exploratory Objectives

## 1.2. Study Design

### 1.2.1. Synopsis of Study Design

This is a Phase 2 multicenter, randomized, double-blind, placebo-controlled, multiple-dose study to evaluate the safety and efficacy of IV administered VIS649 over a 12-month treatment course in participants with IgAN.

Participants will be enrolled from approximately 100 global sites in approximately 16 countries. Enrolled participants will be 18 years of age or older with an IgAN diagnosis confirmed by biopsy.

VIS649 (2, 4, and 8 mg/kg) or placebo will be administered as 12 monthly IV infusions (Months 0-11) as described in the schedule of assessments (Current Version of Protocol). The final efficacy assessments will be taken at the Month 12 Visit (ie, around Day 360, following approximately 12 months of exposure to study drug), and a final safety evaluation will be conducted at Month 16 (ie, approximately 5 months following last study drug dosing). Up to 60 participants (approximately 15 participants in each treatment group) may have a more intensive PK and PD sampling schedule at Months 0-3 and 11-14 (see Current Version of Protocol).

Efficacy assessments will be primarily evaluated by the reduction in uPCR from baseline. The timepoints to be used for uPCR urine collections are referred to as either Schedule 'A' or 'B', depending on whether the uPCR are collected from the 24-hour urine collection (or an intended 24-hour urine sample) (i.e., '24-hour' Schedule A Urine Collection) or not (ie, 'Spot' Schedule B Urine Collection). Schedule A Urine Collection visits include Screening, Days 270 (Month 9), 360 (Month 12) and 485 (Month 16), where Screening would be the Baseline visit. Schedule B Urine Collection visits include Day 1 (pre-infusion) and Days 8, 30, 60, 90, 120, 150, 180, 210, 240, 300 and 330, where Day 1 (pre-infusion) would be the Baseline visit.

Safety assessments will include review of adverse events (AEs) (including hypersensitivity reaction, anaphylactic reaction, and injection site tolerability), physical examinations, clinical laboratory assessments (including biochemistry, hematology, urinalysis, and pregnancy testing), laboratory testing (including serum Ig levels and ADAs), vital sign measurements, and use of concomitant medications.

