### 1.2.2. Randomization Methodology

Participants will be randomly assigned in a 1:1:1:1 allocation ratio to receive VIS649 at 2, 4, or 8 mg/kg or placebo, with approximately 36 participants randomized to each treatment group.

Randomization will be stratified by region (Japan vs Rest of World [ROW]). A target of 12 or more participants are planned to be randomized at Japanese sites. Japanese participants will be randomized with equal allocation and without further stratification. Randomization for ROW will be stratified by screening uPCR (Schedule A,  $\leq 2.0$  g/g vs  $> 2.0$  g/g). Further details about the creation of randomization schemes, and other randomization procedures, can be found in the Randomization Plan (Appendix 1).

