### **3. GENERAL STATISTICAL METHODS**

#### **3.1. Sample Size Justification**

The sample size for this study was calculated assuming a linear dose response (reduction of uPCR) of 0%, 15%, 30%, and 45% in placebo and VIS649 2, 4, and 8 mg/kg groups, respectively. Applying contrasts of -3, -1, 1, and 3 for the corresponding dose levels and analyzing uPCR on the natural log scale, the result is an expected mean change from baseline of 0, -0.163, -0.357, and -0.593 for placebo and VIS649 groups of 2, 4, and 8 mg/kg, respectively. Using an analysis of variance model with contrasts of -3, -1, 1, and 3 for the corresponding groups, a standard deviation (SD) of 0.87, 80% power, a 2-sided type I error rate of 0.05, and accounting for a dropout rate of ~ 20%, the required sample size is 36 participants per group, or 144 participants overall.

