#### 4.4.2. Sensitivity Efficacy Analyses

The annualized slope of eGFR estimated over the course of 12 months. The linear mixed effects model with random effects will be used to compare the annualized slope of eGFR between treatment groups estimated over the course of 12 months. The response variable of the model is the eGFR value at each post baseline visit. The model will be fitted with fixed effects of treatment, time (as a continuous variable), treatment-by-time interaction, strata, baseline eGFR and random effects of intercept and time. The unstructured covariance structure will be used. The annualized eGFR slope by each treatment group, together with SE and 95% CI will be reported. The statistical inference will be based on testing of the difference on the eGFR annualized slope between two treatment groups and estimation of the difference and its 95% CI.

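### The eGFR slope endpoints give a two-reading slope the same weight as a 13-reading slope; the mixed model already in SAP 4.4.2 should be the main slope analysis and should also cover Month 16.

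*SAP*

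**What the plan says.** SAP 1.2.5.2 lists the linear eGFR slope to Month 12 and to Month 16 among the secondary endpoints. SAP 4.4.1.4 derives each slope "respectively across time (days), per subject, using the linear model" of eGFR on days. The slopes "will be compared between placebo and VIS649-treated groups using an ANCOVA model with baseline eGFR as covariate". That section states no weights, no minimum number of readings and no minimum follow-up.

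The analysis set is mITT (SAP 4.4), so one dose is enough for inclusion. SAP 3.10 in general imputes no missing data.

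SAP 4.4.2 adds a sensitivity analysis: "The linear mixed effects model with random effects will be used to compare the annualized slope of eGFR" between treatment groups. It has random effects of intercept and time, and covers 12 months only. No equivalent model is given for the Month 16 slope.

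**The concern.** Ordinary ANCOVA treats every outcome as equally precise. These slopes are not. A completer has about 13 readings over a year, while someone who leaves after the Day 30 visit has two readings 29 days apart. Short series are foreseeable: the sample size was set "accounting for a dropout rate of" about 20%, and Protocol 7.1 only encourages participants who stop dosing to keep attending.

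At stake is precision. The designated slope comparison could have a wider interval than the data warrant, or be moved by one or two very noisy slopes. It could then disagree with its own sensitivity analysis, which handles short series better. The slope bears on a hypothesis that the SAP states in its introduction, that eGFR decline will stabilise.

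**Working it through.** The documents state no standard error, SD or power for the eGFR slope, so there is no figure of the plan's own to reproduce.

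**Inputs from the documents**
- Group size: "with approximately 36 participants randomized to each treatment group" (SAP 1.2.2).
- Creatinine timing: full chemistry at M0, M3, M6, M9, M12 and M15, and "the following tests are required at other visits: sodium, potassium, chloride, bicarbonate, blood urea nitrogen, creatinine, and glucose" (Protocol 1.3). That gives 13 readings to Month 12: Day 1, then Days 30, 60, …, 360.
- Dropout allowance: about 20% (SAP 3.1), or 0.20 × 36 ≈ 7 per group.

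**Assumed, because the documents do not give them**
- Within-person eGFR SD (se): 3 to 5 mL/min/1.73 m².
- True-slope SD (sb): 3 to 8 mL/min/1.73 m² per year.
- Dropout timing: last visit spread evenly over Days 30 to 330.

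**Step 1: error variance of one slope.** Var(slope) = sb² + se²/Sxx, where Sxx is the sum of squared centred visit times in years. Two readings (Days 1 and 30): Sxx = (29²/2)/365.25² = 0.00315, so 1/Sxx = 317. The multiplier 1/Sxx depends only on the schedule.

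| Readings | 1/Sxx (per year²) | Relative to 13 readings | Error SD if se = 5 |
|---|---|---|---|
| 2 | 317.3 | 389 | 89 |
| 3 | 76.6 | 94 | 44 |
| 4 | 30.2 | 37 | 27 |
| 13 | 0.816 | 1 | 4.5 |

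To Month 16, with one further reading at Day 485, a complete series has 1/Sxx = 0.534, so the disparity is larger.

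**Step 2: a worked case (se = 5, sb = 5).** Three of 36 per arm leave, with two, three and four readings.
- Complete slope: 25 + 25 × 0.816 = 45.4. Short slopes: 7,956, 1,941 and 781.
- Equal weights: mean variance = (33 × 45.4 + 7,956 + 1,941 + 781)/36 = 338. SE of an arm difference = √(2 × 338/36) = 4.33 per year.
- Ideal inverse-variance weights: √(2/Σ(1/v)) = √(2/0.7287) = 1.66.
- No early dropouts: √(2 × 45.4/36) = 1.59.

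Simulating this case gave 3.97 (mean model SE) to 4.47 (empirical SD) for the SAP's ANCOVA, against 1.74 to 1.91 for a fitted random-intercept, random-slope model on the same data. If all three leavers have four readings, the equal-weight SE is 2.43. With five, six and seven readings it is 1.88.

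**Step 3: random dropout.** Median SE ratio, equal weights to ideal precision weights, 36 per arm, simulated. The end-of-study (EOS) reading is placed 120 days after the last attended visit and used if it falls by Day 375.

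| Dropout; EOS attendance | se = 3; sb = 3, 5, 8 | se = 5; sb = 3, 5, 8 |
|---|---|---|
| 20%; none | 2.10, 1.65, 1.32 | 2.50, 2.10, 1.68 |
| 20%; half | 1.54, 1.31, 1.17 | 1.80, 1.62, 1.35 |
| 20%; all | 1.08, 1.03, 1.01 | 1.13, 1.08, 1.04 |
| 5%; none | 1.19, 1.09, 1.03 | 1.28, 1.22, 1.10 |
| 5%; half | 1.05, 1.02, 1.01 | 1.09, 1.05, 1.02 |

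The ratio turns largely on whether a two-reading series is present, so the medians move somewhat with the set-up. For half attendance I quote about 1.1 to 1.9.

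**Step 4: why one late reading matters.** Days 1 and 30 alone give an error SD of 89 at se = 5. Adding Day 150 makes 1/Sxx = 10.7 and the error SD 5 × √10.7 = 16.

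**The case against.** The strongest reply is that the plan already limits short series. Protocol Table 1 requires early-termination assessments, and a participant who stops early is encouraged to attend the remaining visits and an EOS visit about 120 days after the last dose. Chemistry is drawn at both. SAP 3.11 relabels early termination and EOS visits by their actual month, so they can enter the Month 12 slope. This stands: with full EOS attendance the inflation nearly disappears. Attendance is encouraged, not assured, so the weakness remains but its size is uncertain.

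A reader might infer that the standard error will typically double, or that every arm will contain a two-reading slope. The documents support neither. The 20% is an allowance for the uPCR sample size, not a forecast of short eGFR series. Even at 20% even dropout over 11 possible last visits, the chance that a given arm has a two-reading series is 1 − (1 − 0.20/11)³⁶ = 0.48, and the chance that all four arms do is 0.48⁴, about 5%.

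Two further replies have weight. First, this is a loss of efficiency, not a bias, and eGFR change at Months 12 and 16 is separately analysed by MMRM (SAP 4.4.1.3). Second, equal weighting is robust when dropout depends on the true slope, which is possible because Protocol 7.1 lets the investigator stop dosing for sustained eGFR decline. In an illustrative simulation with a true difference of 4.0 per year and steeper decliners leaving more often, equal weights gave 3.99 and inverse-variance weights 3.69. That shift is small beside the possible gain in precision, but it is a reason to keep the unweighted analysis as a check.

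**Conclusion.** The point holds as one about precision. Following SAP 4.4.1.4 exactly gives a slope comparison that can be needlessly imprecise. The variance multiples of 389, 94 and 37 need no outside figure.

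The effect on the standard error rests on the assumed SDs and dropout pattern. It is about 1.3 to 2.5 times at 20% dropout with no later readings, about 1.1 to 1.9 times if half of dropouts attend EOS, and close to 1 if all attend or if dropout is near 5% with some attendance. Doubling is an upper scenario.

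It would also be wrong to infer that the trial's efficacy claim is at risk. SAP 3.7 makes secondary tests descriptive, and the primary uPCR test does not use these slopes. Rating: cheap improvement.

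**What to change.** - Make the random-intercept, random-slope model of SAP 4.4.2 the main analysis for the eGFR slope to Month 12.
- Specify the same model for the slope to Month 16, which SAP 4.4.2 does not cover.
- Keep the per-participant slope ANCOVA as a supportive check, and report the number of readings behind each slope.
- Do not limit that check to participants with at least 6 months of readings: this selects on post-randomisation follow-up.

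The cost is a little SAP wording and some programming; the documents show that the 12-month model is specified, not that it is programmed. The mixed model may shift the estimate slightly if dropout depends on the true slope, and the retained unweighted check would show this. No new data are needed.

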#### 4.4.1.5. Total serum IgA, IgG, and IgM concentrations (mg/dL) in the PD population

Total serum IgA, IgG, and IgM concentrations (mg/dL) percent of baseline and change on the natural log scale, will be summarized descriptively over time, including the geometric mean ( $\pm$  95% CI). The total serum IgA, IgG, and IgM concentrations percent change and percent of baseline will be displayed graphically (mean  $\pm$  SD).

#### 4.4.1.6. Other Endpoints

The secondary efficacy analyses for the following binary endpoint will use a logistic regression model to compare VIS649 2, 4, and 8 mg/kg to placebo (0 mg/kg). Summary statistics, the odds ratio (OR), 95% CIs and p-values for each dose group (2, 4, 8 mg/kg), and pooled dose groups, compared to placebo, will be reported for the following outcomes:

- Number of participants in each group achieving a  $\geq$  30% decline from baseline in 24-hour uPCR (Schedule A), on the log scale, at Months 9, 12, and 16.
- Number of participants in each group achieving reduction in 24-hour urine protein excretion to  $<$  300 mg/day for at least 3 consecutive months at Months 9, 12, and 16 if data is available.

An OR of 1 will indicate that the treatment (2, 4 or 8 mg/kg) does not affect the odds of the outcome (ie, achieving a  $\geq$  30% decline from baseline in uPCR (Schedule A) or achieving reduction in 24-hour urine protein excretion to  $<$  300 mg/day or  $<$  200 mg/mg uPCR (Schedule A) for at least 3 consecutive months at Month 12 whereas and OR  $>$  1 will indicate that the treatment is associated with a higher odds of the outcome and an OR  $<$  1 will indicate that the treatment is associated with a lower odds of the outcome.

#### 4.4.2. Sensitivity Efficacy Analyses

The annualized slope of eGFR estimated over the course of 12 months. The linear mixed effects model with random effects will be used to compare the annualized slope of eGFR between treatment groups estimated over the course of 12 months. The response variable of the model is the eGFR value at each post baseline visit. The model will be fitted with fixed effects of treatment, time (as a continuous variable), treatment-by-time interaction, strata, baseline eGFR and random effects of intercept and time. The unstructured covariance structure will be used. The annualized eGFR slope by each treatment group, together with SE and 95% CI will be reported. The statistical inference will be based on testing of the difference on the eGFR annualized slope between two treatment groups and estimation of the difference and its 95% CI.

### 4.5. Analyses of Exploratory Endpoints

  
All exploratory endpoints (see [Section 1.2.5.3](#)), excluding those specified to be analyzed outside of this SAP, as well as the respective changes from baseline, for each parameter will be summarized descriptively over time by treatment group, including number and percentage of

participants with missing or incomplete assessments at that visit. No formal statistical comparisons will be performed.

